Prospective Study of Colorectal Procedures with the Levita Magnetic Surgical System

Protocol Number: CP006

Revision: A

21 May 2019

Sponsor: Levita Magnetics International Corporation
[name]
Title: CEO and Founder
Email: [contact]
[contact]
[name]

Sponsor Signature:

Sponsor Name: [name]

CONFIDENTIALITY STATEMENT

This study is confidential in nature. All information related to this study is considered proprietary and should not be made available to those not directly involved in this study. Authorized recipients of this information include Investigators and co-Investigators, other health care personnel necessary to conduct the study, and Clinical Investigation Ethics Committees and Institutional Review Boards. The personnel provided with data from this study are hereby informed of its confidential and proprietary nature. Release of these data to individuals other than those listed above requires the prior written permission of Levita Magnetics.

PROTOCOL REVIEW PAGE

STUDY TITLE: Prospective Study of Colorectal Procedures with the Levita Magnetic Surgical System
PROTOCOL: CP006
REVISION: A

Investigator's Statement: I agree to conduct this clinical study in accordance with the design and specific provisions of this protocol; modifications to the study or protocol are acceptable only with an approved protocol amendment. I agree to await Ethics Committee (EC) approval of the protocol and informed consent before initiating the study, to obtain informed consent from subjects prior to their enrollment in the study, to collect and record data as required by this protocol and case report forms, submit all reports as required by this protocol, provide the requested financial information, and to maintain study documentation for the period of time detailed in this protocol.

Investigator Signature:

Date of Signature:

Protocol Synopsis

Title:	Prospective Study of Colorectal Procedures with the Levita Magnetic Surgical System
Study Objective:	The purpose of this study is to evaluate the safety and effectiveness of the Levita Magnetic Surgical System in patients undergoing colorectal procedures.
Study Design:	Prospective, multicenter, single-arm, open label study designed to assess the safety and effectiveness of the Levita Magnetic Surgical System in colorectal procedures
Enrollment Size and Number of Sites:	30 subjects at up to three (3) clinical sites in Chile
Subject Population:	All patients at least 18 years of age presenting for elective colorectal surgery are potential candidates
Primary Safety Endpoint:	All adverse events will be captured and reported. Adverse events will be further summarized by relatedness to the MSS devices and/or procedure, seriousness, and level of severity.
Primary Effectiveness Endpoint:	Ability to adequately retract the colon and, as needed, pericolorectal tissue and/or adjacent organs to achieve an effective exposure of the target tissue. Adequate retraction will be deemed to be achieved if it is not necessary to use another port to insert another instrument to retract the target tissues.
Inclusion Criteria:	Subjects must meet ALL of the following inclusion criteria to be eligible for participation in the study: 
 • Subject is at least 18 years of age • Subject has a BMI of at least 20 kg/m² • Subject is scheduled to undergo elective colorectal procedure • Subject, or authorized representative, signs a written Informed Consent Form (ICF) to participate in the study, prior to any study-required procedures
Exclusion Criteria:	Subjects must be EXCLUDED from participation in this study if ANY of the following exclusion criteria are met: 
 • Subject has a BMI of more than 60 kg/m² • Emergency procedures (e.g., obstruction, severe bleeding or perforation) • Significant comorbidities: e.g. cardiovascular, neuromuscular, chronic obstructive pulmonary disease, and urological disease (renal failure)

	
 • Subjects with pacemakers, defibrillators, or other electromedical implants • Subjects with ferromagnetic implants • Clinical history of impaired coagulation confirmed by abnormal blood tests • Subject has an anatomical abnormality noted after initiation of index procedure that would prevent device use • Subject is pregnant or wishes to become pregnant during the length of study participation • Subject is not likely to comply with the follow-up evaluation schedule • Subject is participating in a clinical trial of another investigational drug or device
Study Duration / Follow-up Period	Subjects will be followed for 30 days post-procedure, with follow-up visits at hospital discharge and at 7 and 30 days post-procedure.
Study Principal Investigator	I. [name] Cleveland Clinic Cleveland OH U.S.A.

1 INTRODUCTION

1.1 Background and Rationale

The Magnetic Surgical System (MSS) has been shown to retract soft tissue and organs and enable a reduction in the number of ports when used in laparoscopic procedures including cholecystectomy (Rivas et al.), bariatric surgery (Guerron et al.) and prostatectomy procedures (Diaz et al) and is cleared for commercial use (FDA clearance) for these indications in the United States. In these procedures, the MSS is used to grasp and retract soft tissues and organs so that the surgeon can visualize and access the target site of the surgery (i.e., gallbladder, liver, prostate or periprostatic tissues, respectively).

Tissue retraction is also needed in colorectal surgical procedures. This study is intended to evaluate the safety and effectiveness of the Magnetic Surgical System in colorectal procedures.

As no dedicated abdominal wall port is needed to use the MSS as a tissue retractor, a reduction in the number of ports required for the surgery, with the attendant benefits of this reduction, is anticipated.

2 SURGICAL SYSTEM DEVICE DESCRIPTION

The Levita Magnetic Surgical System is composed of two hand-held instruments: a Magnetic Grasper and an external Magnetic Controller.

The Magnetic Grasper (**Figure 1**) is comprised of two main components: a detachable Grasper Tip and a Shaft. Once the Magnetic Grasper is inserted and the Grasper Tip grasps the desired tissue, the detachable Grasper Tip can be detached from the Shaft and controlled externally using the Magnetic Controller. Traction of the tissue is maintained through the magnetic field attraction between the Grasper Tip and the Magnetic Controller. The Grasper Tip may be repositioned when needed using the Magnetic Grasper shaft or conventional (non-MSS) graspers. The Magnetic Grasper is compatible with a ≥ 10 mm laparoscopic port.

The Magnetic Controller (**Figure 2**) is a single unit with handles that is held external to the body and emits a magnetic field that attracts the detachable Grasper Tip. Once the Grasper Tip is attached to the desired tissue and detached from the Shaft, the Magnetic Controller is placed external to the body to magnetically attract the Grasper Tip to manipulate the target tissue. Adjusting the distance between the Magnetic Controller and the Grasper Tip will modulate the magnetic attraction used for tissue retraction/manipulation. The Magnetic Controller can then be moved freely, facilitating unrestricted shaft-less tissue retraction. If desired, the user can connect the Magnetic Controller to a

commercially available surgical support arm that is compatible with a hexagon-shaped mounting stem.

Figure 1. Magnetic Grasper

[figure not shown]
[figure not shown]

Figure 2. Magnetic Controller

The Magnetic Grasper is actuated via its handle with two distinct scissor-type motions to open and close the Jaws and to disengage the detachable Grasper Tip from the Shaft. The Magnetic Grasper can be used for retraction in the same manner as a conventional laparoscopic tissue grasper, or its Grasper Tip can be released and used with the external Magnetic Controller. When the Grasper Tip is detached from the Shaft, the Shaft can be removed and retraction of the tissue can be achieved through the magnetic attraction between the Grasper Tip and

the external Magnetic Controller. This access port is therefore available for use with other surgical tools. When the procedure is completed, the Grasper Tip is decoupled from the Magnetic Controller and the Shaft may be reinserted to retrieve the Grasper Tip from the patient.

3 INDICATION FOR USE

The Magnetic Surgical System is designed to grasp and retract the colon, peri-colorectal tissues, and adjacent organs in colorectal procedures to facilitate access to and visualization of the surgical site. The device is indicated for use in patients within a BMI range of 20 - 60 kg/m².

4 STUDY PURPOSE AND OBJECTIVE

The purpose of this study is to evaluate the safety and effectiveness of the Magnetic Surgical System as a soft tissue and organ retractor in colorectal procedures.

5 STUDY ENDPOINTS

The following endpoints will be evaluated in all enrolled subjects who undergo colorectal procedures using the Magnetic Surgical System.

5.1 Primary Safety Endpoint

All adverse events will be captured and reported. Adverse events will be further summarized by relatedness to the MSS devices and/or procedure, seriousness, and level of severity.

5.2 Primary Effectiveness Endpoint

Ability to adequately retract the colon and, as needed, peri-colorectal tissue and/or adjacent organs to achieve an effective exposure of the target tissue.

Adequate retraction will be deemed to be achieved if it is not necessary to use another port to insert another instrument to retract the target tissues.

Other Outcome Assessments

- Operative time
- Number of ports/incisions, and as compared to surgeon's standard of care (SOC) for this surgery type
- Time spent in the Post Anesthesia Care Unit (PACU)
- Length of stay (LOS) (time from admittance to post-anesthesia care unit until hospital discharge)
- Conversion rate (conversion to an open procedure due to inadequate MSS performance)
- Estimated blood loss
- Surgical Site Infection (SSI) rates

- Device malfunctions
- Subject satisfaction
- Investigator satisfaction with the MSS's ability to retract intended tissues and facilitate visualization of surgical site

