7.4 Procedure

The Investigator will perform the surgical procedure in accordance with the methods detailed in the Instructions for Use (IFU).

The following intra-operative data will be collected:

- General anesthesia time
- Operative time (from the first incision to the last suture's placement)
- Device and procedure observations
- Conversion to open surgical procedure and reason for conversion
- Number of ports utilized
- Number of ports typically utilized according to surgeon's SOC for specific surgical procedure
- The need for an additional port to place another retractor to retract the colon, peri-colorectal tissues or adjacent organs
- Estimated blood loss
- Video recording of the overall procedure
- Adverse events

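### The primary effectiveness rule depends on port need alone and does not say that a conversion to open surgery for inadequate MSS performance is a failure

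*Combined protocol and SAP*

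**What the plan says.** Section 5.2 defines the primary effectiveness endpoint in two steps. The first sentence gives the concept: the device should retract the colon and, where required, nearby tissue and organs "to achieve an effective exposure of the target tissue". The second sentence makes it operational: "Adequate retraction will be deemed to be achieved if it is not necessary to use another port to insert another instrument" for retraction. The synopsis carries the same rule, with retraction adequate "if it is not necessary to use another port to insert another instrument to retract the target tissues".

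Still under section 5.2, the list of Other Outcome Assessments includes "Conversion rate (conversion to an open procedure due to inadequate MSS performance"). It is a separate outcome, with no reference back to the primary rule.

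Section 7.4 collects two distinct intra-operative items that bear on this: "The need for an additional port to place another retractor to retract the colon, peri-colorectal tissues or adjacent organs", and "Conversion to open surgical procedure and reason for conversion". It also collects "Device and procedure observations" and "Video recording of the overall procedure".

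The opening of section 5 applies the endpoints to every enrolled subject operated on with the MSS. Section 9.1 plans descriptive summaries, and section 9.2 states that no formal sample size calculation was done. Neither section says how a converted case is scored on the primary endpoint.

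**The concern.** The protocol foresees that the MSS may perform so poorly that the surgeon opens the abdomen. It gives that event its own outcome but does not say what it means for the primary endpoint. Port need is the only stated test of adequacy, so a conversion affects the result only if a need for another port was also recorded. A surgeon may go straight from inadequate magnetic retraction to an open procedure without that happening.

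This is the sole primary effectiveness measure, in a single-arm, open-label study. With no comparator, test or performance goal, the observed success proportion is the effectiveness result. Section 9.2 expects 30 subjects to give ample evidence of safe and effective use, and section 14.11 allows for use in regulatory submissions. A success count that includes subjects in whom the device's retraction failed would not mean what a reader takes it to mean. The independent adjudicator described in sections 11.1 and 13.1 reviews adverse events only. No independent review of effectiveness scoring is described, so the written rule carries the weight.

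**Working it through.** The plan gives no figure to reproduce: the 30 subjects are not derived from an error rate, a power, an expected success rate or a performance goal. The check is therefore a reading of the rule case by case, followed by simple arithmetic.

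**Step 1. Who is scored.** Under section 5, a subject in whom the MSS was used and who was then converted stays in the denominator. No text excludes such a subject.

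**Step 2. Apply the rule to the four possible cases.** The inputs are the two separate items in section 7.4: need for another port, and conversion with its reason.

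| Need for another port recorded | Converted to open for inadequate MSS performance | Result under the port rule | Agrees with the effective-exposure sentence? |
|---|---|---|---|
| No | No | Success | Yes, if exposure was effective |
| Yes | No | Failure | Yes |
| Yes | Yes | Failure | Yes |
| No | Yes | Success | No |

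Only the last row is a problem. The first sentence of section 5.2 points to failure and the operational sentence gives success. No text says which prevails.

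**Step 3. Size of one case.** Input: n = 30, the target maximum in section 6.2. Each last-row case scored as a success adds 1/30 = 3.33 percentage points to the reported rate.

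**Step 4. Illustration.** Assume no subject has a recorded need for another port and c subjects fall in the last row. As written, the rate is 30/30 = 100%. With such conversions counted as failures it is (30 − c)/30:

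- c = 1: 29/30 = 96.7%
- c = 2: 28/30 = 93.3%
- c = 3: 27/30 = 90.0%

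The values of c are assumptions; the documents give none.

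**Step 5. Could it arise at all in 30 subjects?** If the probability of a last-row case is p per subject, the chance of at least one is 1 − (1 − p)^30. Since the documents give no p, a range is shown: 45.5% at p = 2%, 78.5% at p = 5% and 95.8% at p = 10%. These p values are also assumptions. They refer to the narrow last-row event, not to all conversions.

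**The case against.** The strongest case for the plan has four parts.

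- **The gap is narrow.** The rule asks whether another port was necessary, not merely whether one was placed, and section 7.4 records the need. Many cases of inadequate retraction will show that need and already be failures. This stands. It limits the point to direct conversions with no port need recorded, but it does not remove them: the two items are recorded separately and neither implies the other.
- **Common sense would score the case as a failure.** The effective-exposure sentence supports that. However, the operational sentence says when adequacy is deemed achieved, and nothing ranks the two.
- **Nothing is hidden.** Device-attributed conversions are reported as their own rate, the reason is collected, and the procedure is filmed. This also stands, and it means that the gap lies in the scoring rule and not in the data. Separate reporting does not correct the primary count, though, and no cross-tabulation of the two outcomes is planned.
- **The study is descriptive.** No test, performance goal or confidence interval is planned, so no decision threshold is crossed. This is correct and caps the severity.

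A reader might also infer that the port wording is a second loophole. Section 5.2 speaks of another port and section 7.4 of an additional port, so a conventional retractor brought in through an existing port might seem to fail under one section and succeed under the other. The documents do not support that. Section 7.4 is a list of data items and contains no success rule, so it cannot give an opposite verdict. The two phrases read naturally as synonyms, given the aim of fewer ports in section 1.1. Nor do the documents give sites the scoring of the endpoint: under section 14.11 the sponsor analyses and reports the data.

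**Conclusion.** The point holds for conversion. The stated rule can score a device-attributed conversion to open surgery as a primary success, against the purpose stated in the same endpoint. It should be fixed, because it is a defined rule that can give a wrong result in a situation the protocol itself anticipates.

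The effect is 3.3 percentage points on the headline success rate per such case at n = 30. How many cases would arise is unknown. The conclusion rests on the literal reading of the operational sentence and on the converted subject remaining in the analysed group, as section 5 indicates. Error rates, power and sample size are not affected, since none is specified.

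Two wider readings should be resisted. The port-based criterion is not itself faulty, because it matches the expected benefit in section 1.1. Use of a conventional grasper is not in itself a failure either: section 2 allows one for repositioning the Grasper Tip, and nothing in the endpoint makes takeover through an existing port a failure. The difference in port wording is a matter of consistency only.

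**What to change.** In the synopsis and in section 5.2, add one sentence directly after the port rule: conversion to an open procedure due to inadequate MSS performance, including inadequate retraction or exposure, is a primary effectiveness failure whether or not a need for another port was recorded. Classify the case from the reason for conversion already collected under section 7.4.

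As a minor wording change, use one port phrase in the synopsis, section 5.2 and section 7.4, without altering what the endpoint measures.

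The cost is one sentence in two places and one harmonised phrase. No extra subjects, visits, procedures or data items are needed. The drawback for the sponsor is that the reported success rate may be slightly lower, by 3.3 points for each such case among 30 subjects.

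### The primary success rule looks only at whether another port was needed, so inadequate MSS retraction made good by a non-MSS instrument through a port already in place is scored as an MSS success

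*Combined protocol and SAP*

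**What the plan says.** Section 4 sets the purpose: to evaluate the MSS as a retractor of soft tissue and organs in colorectal procedures. Section 5.2 names the primary effectiveness endpoint as the ability to retract adequately "to achieve an effective exposure of the target tissue". It then makes this operational: retraction is deemed adequate "if it is not necessary to use another port to insert another instrument to retract the target tissues". The synopsis has the same rule, and neither place adds a further condition.

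Section 2 bears on the rule in three ways:
- Once the tip is detached and the shaft withdrawn: "This access port is therefore available for use with other surgical tools".
- Ordinary graspers are expected in the field: "The Grasper Tip may be repositioned when needed using the Magnetic Grasper shaft or conventional (non-MSS) graspers".
- The device may also be used on its shaft: "The Magnetic Grasper can be used for retraction in the same manner as a conventional laparoscopic tissue grasper".

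In section 7.4 the item that matches the rule is "The need for an additional port to place another retractor to retract the colon, peri-colorectal tissues or adjacent organs". That section also lists the number of ports used, "Number of ports typically utilized according to surgeon's SOC for specific surgical procedure", device and procedure observations, and a video of the procedure. Investigator satisfaction with retraction is collected under section 7.5, and device deficiencies are documented under section 12.6. Section 5.2 lists conversion, malfunctions and satisfaction among the other outcomes, outside the success rule.

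The analysis is descriptive (section 9.1). No sample size calculation was made (section 9.2), and the target maximum is 30 subjects in a single arm (sections 6.1 and 6.2).

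**The concern.** The endpoint is meant to show that the MSS retracts adequately. The rule asks something narrower: whether a further port was needed for a further retracting instrument. The two come apart when the MSS holds poorly but a port already in place can take an ordinary grasper. The surgeon finishes the retraction with that grasper, no port is added, and the subject is scored as a success for a device that did not do the job.

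To that extent the primary rate would reflect spare capacity in the existing ports as well as device performance. The study has no control arm in which the same rule could be seen at work, and section 14.11 says the results may support regulatory submissions. A reader of the reported rate would take it as evidence about the MSS alone.

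**Working it through.** **Step 1. Does the gap depend on how the rule is read?** The words on another port can be taken in two ways. Reading A: a port added to those already placed. Reading B: any port other than the one through which the MSS entered. Suppose MSS retraction was inadequate and a non-MSS instrument then retracted the target tissue.

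| Route of the non-MSS instrument | Reading A | Reading B |
|---|---|---|
| Newly added port | failure | failure |
| A different port already in place | success | failure |
| The freed MSS entry port | success | success |

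The section 7.4 item speaks of an additional port, which favours reading A. On reading B the last row remains, because section 2 makes that port available. The gap is therefore present on both readings and wider on A. No starting number or layout of ports is fixed, so a surgeon may begin with the usual ports in place.

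**Step 2. Does anything else in the plan close it?** The opening sentence of 5.2 refers to effective exposure, but the sentence that follows replaces that judgement with the port question. Port counts do not show which instrument held the tissue. Observations, video, investigator satisfaction and deficiency reports could reveal a rescue, but no section links any of them to the success rule or requires them to be reviewed for this purpose.

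**Step 3. Direction.** Let n be the subjects treated, S those who pass the port rule, and k those among the S in whom a non-MSS instrument through an existing port made good inadequate MSS retraction.

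- Rate under the plan: S/n
- Rate with these cases as failures: (S − k)/n
- Difference: k/n, which is never negative

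**Step 4. Size.** The plan states no expected rate, performance goal or interval, so there is no figure of its own to reproduce. Inputs: n = 30 (section 6.2, assuming the target is reached) and S = 30 (assumed, for illustration). The values of k are assumptions; the documents give none. One case is worth 1/30 = 3.3 points. Intervals are exact (Clopper-Pearson) 95% intervals, added here for scale. For 30/30 the lower limit is 0.025^(1/30) = 0.884.

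| k (assumed) | Rate under the plan | Rate with rescues as failures | Exact 95% interval for the latter |
|---|---|---|---|
| 0 | 30/30 = 100% | 30/30 = 100% | 88.4% to 100% |
| 1 | 30/30 = 100% | 29/30 = 96.7% | 82.8% to 99.9% |
| 3 | 30/30 = 100% | 27/30 = 90.0% | 73.5% to 97.9% |
| 6 | 30/30 = 100% | 24/30 = 80.0% | 61.4% to 92.3% |

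The rate under the plan stays the same in every row, because the rule does not respond to k.

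**The case against.** The strongest case for the plan is that avoiding a retraction port is the benefit the device is meant to bring (sections 1.1 and 8.1). A port criterion is objective, easy to record and tied to that claim. This stands as a reason to keep reporting the port-only rate. It does not make that rate a measure of adequate MSS retraction, since it can be met when the device fails.

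Three further objections limit the point, and each is right:

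- **Detectability.** A reader might infer that such rescues could never be found in the study data. The documents do not support that. Video, observations, investigator satisfaction and deficiency reports are all collected. What is missing is a dedicated item and any link to scoring.
- **On-shaft use.** A reader might infer that using the Magnetic Grasper on its shaft is the same kind of rescue. Section 2 presents it as an intended mode of the MSS, and section 4 does not confine the purpose to magnetic retraction. It is not non-MSS retraction and should not be scored as failure.
- **Complementary handling.** A reader might conclude that any non-MSS instrument holding target tissue should be a failure. Section 2 foresees other tools in the freed port, and section 3 says the device is to facilitate access and visualization. Failing every such case would bias the rate downward.

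The Instructions for Use, which sections 7.4 and 11.3 require to be followed, are not among the documents and might restrict concurrent retraction. The protocol's own text does not.

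**Conclusion.** The gap in the rule is real and follows from the wording alone. A case in which MSS retraction was inadequate and a non-MSS instrument was passed through a port already in place is scored as a success: certainly through the freed entry port, and through any existing port on the section 7.4 wording.

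The error can run only upward, at 3.3 points per case with 30 treated subjects. The illustrative range of 96.7% to 80.0% rests on an assumed 1 to 6 cases and on all 30 passing the port rule. Nothing in the documents says how often such rescue would happen, so they do not support a statement that the reported rate will be inflated by any particular amount, or that rescue would be common.

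Because the plan has no performance goal or test, no pre-specified decision turns on the result. The point is one that should be fixed; the documents do not show that the study would fail without the change.

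**What to change.** In section 5.2 and the synopsis, add that adequate retraction is not achieved if a non-MSS instrument, through any port, existing or added, was used to retract the target tissue because MSS retraction was inadequate. State that repositioning the tip and routine complementary tissue handling do not count as failure. State also that on-shaft use of the Magnetic Grasper is recorded but not scored as failure.

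In section 7.4, add to the case report form:

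- non-MSS instrument used to retract target tissue because of inadequate MSS retraction (yes/no; existing or added port; reason)
- tip detached and magnetically retracted (yes/no)

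Name the procedure video as source, and report the port-only rate alongside as a supporting result. Settle this before enrolment so that the items are completed in the same way throughout.

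The cost is a wording change and a few form fields, with no added procedures or subjects. The change affects scoring only and does not tell the surgeon what to do. There are two drawbacks. The reported success rate may be lower. The reason for non-MSS retraction also depends on the surgeon's judgement, which the video can be used to check.
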